#### Background & Purpose of the Research

Describe the purpose, specific aims or objectives and specify the hypotheses or research questions to be studied:

Aim 1: Quantify the neurological and functional improvements due to BCI-FES dorsiflexion therapy compared to dose- and intensity-matched conventional therapy. Hypothesis: The neural repair mechanisms underlying BCI-FES dorsiflexion therapy will lead to improvements in neurological and functional outcomes that are greater and longer-lasting than those achieved by dose-matched conventional therapy. Aim 2: Identify stroke features that are linked to responsiveness to BCI-FES dorsiflexion therapy. Hypothesis: Based on preliminary studies, baseline gait velocity, dorsiflexion AROM/torque, TA muscle electromyogram (EMG) and motor evoked potentials, the magnitude of EEG alpha- and beta-band ERD/ERS during attempted dorsiflexion, and sensory function will influence the response to BCI-FES dorsiflexion therapy. Aim 3: Investigate the mechanism of action of BCI-FES dorsiflexion therapy. Hypothesis: BCI-FES therapy reinforces the connectivity between foot M1 and the  $\alpha$ -MN due to Hebbian plasticity. The study will have a significant impact in rehabilitative neuroscience, clinical neurorehabilitation,

Provide the scientific or scholarly rationale for the research and describe the relevant background information and the specific gaps in current knowledge that this study intends to address:

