## Study Design

Include an explanation of the study design (e.g., randomized placebo-controlled, cross-over, cross-sectional, longitudinal, etc.) and, if appropriate, describe stratification/randomization/blinding scheme:

Aim 1 is a parallel, 2-arm randomized controlled Phase 2 clinical trial. Aim 3 is a randomized, 2-arm randomized controlled study (not a clinical trial). They will produce the following study groups 1. Aim 1 – randomization 1:1 between 2 groups as follows: a. Group 1 (40 subjects): undergoing multiple sessions of 1 hour BCI-FES therapy followed by 1 hour of conventional physical therapy b. Group 2(40 subjects): undergoing multiple sessions of 2 hour conventional physical therapy sessions 2. Aim 3 – randomization 1:1 between 2 groups as follows: a. Group 3 (10 subjects): BCI-FES therapy (no conventional physical therapy) b. Group 4 (10 subjects): BCI-robotic orthosis therapy (no conventional physical therapy) BCI-FES therapy: Group 1 subjects will undergo placement of a 4-channel EEG cap using standard technique (Cz, Cpz, C1, C2) and be connected to our custom BCI system (from Study 1a). Note that based on Study 3, this electrode selection will likely capture brain areas subserving dorsiflexion for all stroke subjects. Subjects will provide 5 min of training EEG data as they engage in alternating epochs of idling and attempted foot dorsiflexion (of the paretic side). The automated software will analyze the data to generate and calibrate a BCI decoder (additional 5-10 mins). In the online phase (involves actively operating the BCI system in real-time), the subjects will perform 20-25 BCI-FES runs (total of 1 hour). In each run, subjects will follow 10 alternating epochs of 10-s long idling/dorsiflexion textual cues, and respond by either idling or attempting dorsiflexion to elicit BCI-FES mediated contractions of the TA muscle. A total of 12 sessions will be performed at a rate of 3x/week (over 4 weeks). Each BCI-FES therapy session will be followed by 1 hour of conventional physiotherapy as described below. Conventional Physical Therapy: This will consist of a standardized regimen of activities typical of conventional post-stroke gait therapy, including passive/active range of motion exercises (to reduce/prevent excessive plantarflexor contractures), lower-extremity muscle strengthening, and a progression from treadmill to overground walking exercises. A total of 12 sessions will be performed at 3x/week. For Group 1, conventional physiotherapy will immediately follow each BCI-FES session and last for 1 hour. In the dose-matched control group (Group 2), it will be 2 hours/session. Subjects will not be allowed to undergo outside physiotherapy for the entire

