
study. A commercial company will be used to assign patients a 30 minute home exercise program to be completed 4 times a week with compliance assessed via non-invasive sensors. For those without a mobile device, a pen and paper version of the home exercise program will also be available. Aim 3: The aim is designed as a randomized controlled study with two arms: BCI-FES dorsiflexion therapy and BCI-robotic orthosis therapy. A total of 20 subjects will be recruited and randomized with 1:1 ratio into the two arms. The primary outcome is gait velocity, and the secondary outcomes are ankle torque and active range of motion. The main interest is to evaluate if the correlation between  $M1 \rightarrow EMG$ ,  $w$ , (normalized range: 0-1), and gait velocity is different between the two study groups averaged over time after treatment, adjusted for baseline outcome measure. For example, with outcome gait velocity, the analysis will be based on a regression model with group,  $w$ , and their interaction, adjusted for baseline gait velocity. The relationship between both  $w$  with secondary outcomes will be similarly analyzed. TR-NIRS parameters will be measured at the TA muscle of stroke patients while they attempt dorsiflexion while seated with the tibia perpendicular to the ground.

Measurements pertaining to oxygen metabolism at the TA muscle will be acquired by placing the source and detector fibers on the skin surface positioned over the muscle (using the adhesive pads). This setup allows for the collection of metabolic data in real time while either the BCI-FES or BCI-robotic orthosis systems are being used.

Provide precise definitions of the study endpoints and criteria for evaluation; if the primary outcomes are derived from several measurements (i.e., composite variables) or if endpoints are based composite variables, then describe precisely how the composite variables are derived:

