
having TA EMG or no response (no detectable EMG activity after 4 attempts).

3. EEG features: Movement induced EEG ERD/ERS and its spatial distribution in  $\mu$  (8-12 Hz) and  $\beta$  (13-30 Hz) bands may change after stroke. Since BCI-FES therapy depends upon and possibly alters  $\mu$  and  $\beta$  modulation, it is important to understand how the baseline ERD/ERS magnitude affects response to the therapy. EEG prior to the first BCI-FES session will be taken from Aim 1.

4. Nottingham Sensory Score: Baseline sensory impairment, as assessed by the Nottingham sensory system, can help determine if BCI-FES therapy can circumvent this requirement or not. Note that subjects will be informed that they are to refrain from starting any additional new physical therapies or other studies in stroke recovery for the entire duration of the study (including post-therapy visits). Subjects will be informed that those who become involved in outside therapy will be removed from the study as this may confound the scientific results.

Aim 3 (Mechanism study, not a clinical trial): In order to elucidate the plasticity mechanism underlying BCI-FES therapy, it is necessary to compare BCI-FES therapy to a control. Hence, two new groups of chronic stroke subjects with foot-drop will be recruited (10 subjects each, same selection criteria as in Aim 1). The first group (Group 3), will undergo BCI-FES therapy as in Aim 1 (no concurrent physiotherapy). The second group (Group 4), will undergo BCI-robotic orthosis therapy. This comparison will allow us to determine if the mechanism of BCI-FES therapy is via enhanced sensory feedback, or via co-incident activation of upper and lower motor neurons. BCI-robotic orthosis therapy is similar to BCI-FES therapy, except that the FES system is replaced by a robotic orthosis that dorsiflexes the foot when attempted dorsiflexion is detected from EEG. The use of a BCI-robotic allows us to test if sensory feedback is the primary driver of the neurological improvements or if co-incident firing between the brain motor cortex and muscles is the primary driver. It should be noted that BCI-FES and BCI-robot therapies both provide sensory feedback, but only BCI-FES provides co-incident firing between the brain motor cortex and the muscles. The primary outcome examined here will also be gait velocity. Other secondary outcomes include gait endurance and TA volitional EMG, as described above.

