The BCI-FES system will be used to deliver a form of BCI-based physiotherapy to stroke patients participating in the study. Robotic exoskeleton sensory task: The robotic exoskeleton (same as used in already part of the study for Group 3 and 4) will be used for a foot position matching task. The subject will bear one robotic exoskeleton placed on each foot for the sensory testing. The foot position will be randomly moved by the exoskeleton and the subject will indicate when the ankle positions overlap. This will be repeated for a total of 25 times. BCI-robotic orthosis therapy is similar to BCI-FES therapy, except that the FES system is replaced by a robotic orthosis that dorsiflexes the foot when attempted dorsiflexion is detected from EEG. The use of a BCI-robotic allows us to test if sensory feedback is the primary driver of the neurological improvements or if co-incident firing between the brain motor cortex and muscles is the primary driver. It should be noted that BCI-FES and BCI-robot therapies both provide sensory feedback, but only BCI-FES provides co-incident firing between the brain motor cortex and the muscles.

Does this device have an Instructions for Use/User Manual/Product Brochure?

No

**REQUIRED!** Submit the Instructions for Use, User Manual or Product Brochure in the Attachments Section

Include information to describe how it works and the foreseeable risks associated with its use: Risks and side effects related to the BCI-Robot operation include those which are: - Discomfort with wearing EEG electrodes (unlikely) - Increased falls (highly unlikely) - Fatigue (unlikely)

Is the device a [medical device](#)?

Yes, this device is a medical device

If "no", for minimal risk studies and the device is intended to be used in a clinical setting, provide justification for selecting "no", citing any regulatory guidance as applicable:

Are you testing the safety and/or efficacy of this device?

Yes, we are assessing the safety and/or efficacy of this medical device; this is a clinical investigation

If "no", for minimal risk research and if the device is the object of the investigation, provide justification for selecting "no", citing any regulatory guidance as applicable:

Is the device approved for marketing in the United States?

No

How is the device approved in the United States?

**REQUIRED!** Submit FDA Documentation in the Attachments Section

Select one of the following:

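### Aim 3 cannot attribute a BCI-FES advantage to co-incident activation, because electrical stimulation and co-incidence are present or absent together in every group

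*Combined protocol and SAP*

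**What the plan says.** The Aim 3 hypothesis under Background & Purpose of the Research is Hebbian: "BCI-FES therapy reinforces the connectivity between foot M1 and the" spinal motor neurons. To test it, Study Design sets up two groups:

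- "Group 3 (10 subjects): BCI-FES therapy (no conventional physical therapy")
- "Group 4 (10 subjects): BCI-robotic orthosis therapy (no conventional physical therapy")

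The control is described as the same therapy, "except that the FES system is replaced by a robotic orthosis that dorsiflexes the foot when attempted dorsiflexion is detected from EEG". On allocation: "A total of 20 subjects will be recruited and randomized with 1:1 ratio into the two arms".

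The inference is stated firmly: "This comparison will allow us to determine if the mechanism of BCI-FES therapy is via enhanced sensory feedback, or via co-incident activation". The plan grants that both therapies give sensory feedback and names one distinguishing feature: "but only BCI-FES provides co-incident firing between the brain motor cortex and the muscles". The robotic orthosis entry under Medical Devices repeats this ("only BCI-FES provides co-incident firing between the brain motor cortex and the muscles") and presents the comparison as a test of which of the two is the primary driver.

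The main Aim 3 analysis (Study Design and Statistical Considerations) is a regression of gait velocity on group, w, their interaction and baseline gait velocity, where w is the coherence between the Cz EEG and the tibialis anterior EMG. Study Design reads a group difference in the w–gait relationship as evidence on mechanism, though in more cautious terms.

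**The concern.** Replacing FES with a robot removes co-incident firing, but it also removes all electrical stimulation of the tibialis anterior and the contraction it evokes. The plan offers a choice between two explanations, sensory feedback and co-incident activation. It never names the third: that repeated stimulation of the muscle and nerve has an effect whether or not it is timed to cortical activity.

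At stake is the conclusion that Aim 3 exists to deliver. A result favouring BCI-FES would, on the plan's wording, be reported as support for Hebbian plasticity, although an effect of stimulation alone is equally compatible with it.

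**Working it through.** **Step 1. The plan's own figure.** Statistical Considerations gives 82% power at n = 20 for an R-square of 0.16 for the interaction, with 0.5 from three other variables. The 0.05 level is stated for Aims 1 and 2 and assumed here for Aim 3.

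- f² = 0.16 / (1 − 0.5 − 0.16) = 0.16 / 0.34 = 0.471
- Noncentrality = 20 × 0.471 = 9.41
- Degrees of freedom: 1 and 20 − 4 − 1 = 15
- Power = 81.8%

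The stated 82% reproduces and is not in question. It is the power to detect an interaction and says nothing about what causes one.

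**Step 2. What each group receives**, from Study Design. S is electrical stimulation of the tibialis anterior; C is co-incident cortex–muscle firing as the plan describes it.

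| Group | Therapy | S | C |
|---|---|---|---|
| 1 (Aim 1) | BCI-FES, then 1 hour conventional therapy | 1 | 1 |
| 2 (Aim 1) | 2 hours conventional therapy | 0 | 0 |
| 3 (Aim 3) | BCI-FES only | 1 | 1 |
| 4 (Aim 3) | BCI-robotic orthosis only | 0 | 0 |

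S equals C in every row, so bringing in the Aim 1 groups does not help.

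**Step 3. What the arm contrast identifies.** Suppose stimulation adds δS to mean gait velocity and co-incidence adds δC.

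- Mean(Group 3) − Mean(Group 4) = δS + δC

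The matrix with columns (intercept, S, C) has rows (1, 1, 1) for Group 3 and (1, 0, 0) for Group 4. Its rank is 2 for 3 parameters. A group with stimulation but no co-incidence, row (1, 1, 0), would raise the rank to 3. No such group exists in either aim.

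**Step 4. What the interaction identifies.** With G = 1 for BCI-FES, the planned model is

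- gait velocity = b0 + b1·G + b2·w + b3·(G × w) + b4·baseline

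Let stimulation change the w slope by γS and co-incidence change it by γC. Because S = C = G, b3 = γS + γC. The interaction carries the same ambiguity as the main effect.

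**Step 5. Sample size is irrelevant to this.** The rank does not depend on n. The Progress Report in the renewal form gives 10 randomised in Aim 3. The formula in Step 1 then gives noncentrality 10 × 0.471 = 4.71 on 1 and 5 degrees of freedom, or about 42% power. That makes a positive result less likely. It does not change how one may be attributed.

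**The case against.** Several points can be made for the plan.

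- *The contrast still tests something.* This stands. If BCI-FES does better, BCI-triggered movement feedback of the kind the robot gives is not sufficient by itself. A reader might infer that Aim 3 is uninformative about mechanism; that goes too far.
- *Stimulation alone need not produce the main result.* This also stands in part. A stronger muscle could raise walking speed in one arm without changing how speed relates to w. A reader might go further and infer that stimulation raises EMG amplitude and so inflates w. The documents give no support for that: w is a coherence normalised to 0–1, and scaling an amplitude does not by itself change a coherence. The point here needs no such pathway. It is enough that nothing in the design excludes a stimulation effect on either quantity.
- *TR-NIRS compares muscle metabolism between the arms.* This gives a partial view of peripheral effects, but it is measured in the same two groups, so S and C remain inseparable.
- *The wording on w is softer.* True, but the firm statement that the comparison will determine the mechanism, and the either-or choice that follows, remain in the same section.
- *The Background notes that the benefits of orthoses, including FES orthoses, do not persist after removal.* That concerns worn devices. It is not a control for a course of stimulation sessions.
- *Device logs could separate the two.* A reader might infer that relating outcome to the share of stimulation delivered in cued dorsiflexion epochs would isolate co-incidence. It would not. Stimulation is always triggered by EEG, so stimulation in an idle epoch is not shown to be unpaired. The share is essentially decoder accuracy, which may track the ERD/ERS strength and baseline function that the plan itself expects to influence response.

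**Conclusion.** The stated inference is not supported by the design. Stimulation and co-incident activation are fully confounded in Aim 3, and no other group separates them. The conclusion rests only on the group descriptions in the plan and on treating stimulation as a possible cause. It does not assume that stimulation has an effect.

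The size is a matter of identifiability: only the sum of the two effects can be estimated, from the arm contrast or from the interaction. A reader might want to put a figure on how often a stimulation effect would be wrongly credited to co-incidence, by carrying the Aim 1 variance inputs into a simple comparison of the two arms. The documents do not support such a figure. They give no effect size for stimulation alone, and a simple arm difference is not Aim 3's main test.

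The Aim 1 efficacy comparison and the Aim 3 power figure are unaffected.

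**What to change.** Amend the Aim 3 text under Study Design, and the matching primary-driver text in the robotic orthosis entry under Medical Devices, to say that:

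1. Aim 3 compares BCI-FES with BCI-triggered robotic movement.
2. The arms differ in electrical stimulation and evoked contraction as well as in co-incident firing, and stimulation alone is an unresolved alternative explanation.
3. An advantage for BCI-FES may be read as evidence that BCI-triggered movement feedback alone is not sufficient. No Hebbian or co-incidence conclusion will be drawn from the arm contrast or the group-by-w interaction alone.

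Apply the same limit to the sentence in Study Design that interprets the comparison of w–gait correlations.

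If a device-log analysis is added, label it exploratory and non-randomised, adjust it for baseline ERD/ERS, baseline gait velocity and group, and do not let it license the mechanistic claim. It would also depend on the logs having been kept, which the documents do not state.

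The Progress Report says enrolment and treatment are complete and that final assessments and analysis remain. A further arm is therefore not available in this study, but the wording can still be settled, and dated, before the Aim 3 results are interpreted. The cost is a few sentences. The downside is a narrower claim.

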#### **Statistical Considerations**

Is a statistical analysis plan appropriate for this qualitative study design?

Yes

Describe the statistical methods for the stated specific aims and hypotheses. Your analysis plans should match the stated study specific aims and hypotheses:

Aim 1: The study design is a parallel randomized controlled trial with two arms: BCI-FES dorsiflexion therapy and dose-matched conventional physical therapy. A total of 80 subjects (which includes 10% attrition) will be randomized with 1:1 ratio into the two study arms. The primary outcome is gait velocity and the secondary outcomes are gait endurance, fall frequency, leg motor FM score, and dorsiflexion AROM and torque. Outcomes measures will be evaluated at baseline, weekly during therapy, immediately post-intervention, and 1- month and 3-months post-therapy. The primary efficacy analysis (with intent-to-treat analysis with respect to treatment randomized) will be based on a linear mixed model (LMM) with gait velocity measured at baseline weeks 1-4 (time 0, 1, 2, 3, and 4) with time, treatment group and group by time interaction assess the difference in the rates of change (improvement) in gait velocity between treatment groups. Model estimation will be based on restricted maximum likelihood (REML) with unstructured covariance among repeated measurements over time. The LMM will also be applied to evaluate group difference for secondary outcomes and secondary endpoints at 1- and 3-months post-therapy. In order to determine if  $\mu$  and  $\beta$  ERD/ERS significantly changes over the 4 weeks of therapy, the ERD and ERS magnitude will be calculated for each EEG channel across all attempted dorsiflexion epochs, and for each assessment. The Mann-Whitney U test will be used to determine if any significant changes in the magnitude of ERD/ERS at each assessment with respect to the baseline. Based on the findings, each subject will be categorized as demonstrating significant changes in ERD/ERS or not. Next, all subjects will also be categorized on whether they experienced a detectable increase in gait velocity (defined as an increase in gait velocity of  $>0.16$  m/s with respect to baseline). A Chi-square test will be used to assess if there is a difference between the proportion of those with changes in ERD/ERS magnitude in those who had gait improvement within the BCI- FES therapy group. This will also be repeated for the control group. In addition, to determine if the presence of significant ERD/ERS changes was affected by group, the Chi-square test will be repeated by using BCI-FES group as the observation and the control group as the expected values. Aim 2: Data from Aim 1 will be used for analysis in this aim. The primary outcome is gait velocity immediately post-BCI-FES therapy, and the secondary outcomes are the same as in Aim 1. To test whether specific stroke features (e.g. baseline gait velocity, dorsiflexion AROM, etc.) modify response to treatment over

treatment duration, a LMM model with three-way interaction (group, time, modifying factor) will be used to test whether the slope of the three-factor interaction is zero (specific stroke feature does not modify response to treatment). Aim 3: The aim is designed as a randomized controlled study with two arms: BCI-FES dorsiflexion therapy and BCI-robotic orthosis therapy. A total of 20 subjects will be recruited and randomized with 1:1 ratio into the two arms. The primary outcome is gait velocity, and the secondary outcomes are ankle torque and active range of motion. The main interest is to evaluate if the correlation between  $M1 \rightarrow \text{EMG}$ ,  $w$ , (normalized range: 0-1), and gait velocity is different between the two study groups averaged over time after treatment, adjusted for baseline outcome measure. For example, with outcome gait velocity, the analysis will be based on a regression model with group,  $w$ , and their interaction, adjusted for baseline gait velocity. The relationship between both  $w$  with secondary outcomes will be similarly analyzed.

Describe the statistical method(s) that will be used to analyze the primary outcome(s) or endpoints:

The primary statistical methods for primary outcome, gait velocity, is already described in Aim 1 above.

If appropriate describe secondary or post hoc analyses of primary outcome(s) or other exploratory analysis and if necessary, provide a breakdown of the methods used per outcome or endpoint:

The statistical method for secondary outcome measures is similar to the primary outcome, and is already described in Aim 1 and 2 above.

**Sample Size Determination:** Explain how the overall target sample size was determined (e.g., power analysis; precision estimation), providing justification of the effect size for the primary outcome based on preliminary data, current knowledge/literature and/or cost consideration; if appropriate, provide sample size justification for secondary outcomes. Power analysis should (at least) match the primary outcome/endpoint:

**Power Analysis:** For Aims 1 and 2, the power analysis was based on a LMM with two treatment groups and 5 repeated measures (baseline and after weeks 1-4) with a significance level of 0.05. Previous studies have examined the clinically meaningful gait improvement (minimal clinically important difference) of 0.16 m/s, including a multicenter randomized clinical trial that includes conventional physical therapy. Thus, to ensure clinically meaningful effect size, we assume conventional therapy will have an improvement of 0.25 m/s after 4 weeks of treatment. Data from prior studies as well as our own preliminary data (n=9) found that the between-subject variance in gait velocity of about 0.16 m/s and the within-subject correlation of about 0.95. Table 1 below shows the power to detect improvement of BCI-FES over conventional therapy of 30% - 40%. Thus, for the proposed study with n=80 patients (40 per arm) has 92% to 94% power to detect an effect size/improvement of 35% for various between-subject variance (0.15 m/s to 0.17 m/s) in determining treatment efficacy (Aim 1). We note that n=80 total has been intentionally inflated in order to accommodate the objectives of aim 2 to examine modifying factors, such as TA MEP (primary modifying factor), on treatment. That is, for n=30 per arm the power to determine efficacy (aim 1) is 85% for detecting an effect size/improvement of 35% (between-subject variance 0.16 m/s); thus, increasing to n=40 allows for detecting modifying factor on treatment (aim 2) when the interaction effect smaller (effect size 28% can be detected with 79% power). Table 1: Power to detect improvement in gait velocity due to BCI-FES over conventional therapy for n=80 with various between-subject variance (aim 1). Between-Subject Variance Effect Size (Improvement) 0.15 0.16 0.17 30% 87.3% 85.2 % 83.0% 35% 94.5% 93.5% 92.1% 40% 98.3% 97.7% 97.0% Aim 3: Total sample size of n=20 will have 82% power to detect an R-square of 0.16 (attributed to the effect of interest, e.g., w x group) adjusted for baseline measurement and main effects whose total contribution R-square is 0.5 (for 3 independent variables) in a multiple regression model.

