
speaking, such that subject does not speak sufficient English to comply with study procedures 17. Concurrent enrollment in another investigational interventional study 18. Severe depression, defined as Geriatric Depression Scale Score >11: \*\*Because Geriatric Depression scale scores may be difficult to interpret for some patients, at the discretion of the site's study PI, exclusion criterion #17 ("Geriatric Depression score cannot be >11") can be waived) 19. Concurrent use of FES orthosis for gait. 20. A new symptomatic stroke occurs apart from the index stroke during the screening process and prior to randomization If TMS Eligible (note that potential subjects who do not qualify for TMS will not be excluded from the main study, they will only be excluded from undergoing TMS procedures): 21. TMS: Metallic hardware on the scalp (e.g. vascular clips or cranioplasty mesh) 22. TMS: Implanted medication pumps, intracardiac line, or central venous catheter 23. TMS: History of cortical stroke or other cortical lesion such as brain tumor 24. TMS: Prior diagnosis of seizure or epilepsy 25. TMS: Any electrical, mechanical, or magnetic implants 26. TMS: History of neurosurgery 27. TMS: uncontrolled Migraine headaches 28. TMS: Any current medications that affect seizure threshold such as tricyclic antidepressants and neuroleptics 29. TMS: Unstable medical conditions

Is eligibility based on age, gender, pregnancy/childbearing potential, social/ethnic group, or language spoken (e.g., English Speakers only)?

Yes

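### The Aim 1 and Aim 2 powers assume 40 per arm analysed although the 80 randomised already include 10% attrition, and the 79% offered for Aim 2 is not tied to the planned three-way interaction

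*Combined protocol and SAP*

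**What the plan says.** Under Statistical Considerations, the Aim 1 text reads: "A total of 80 subjects (which includes 10% attrition) will be randomized with 1:1 ratio into the two study arms". The primary analysis is an intention-to-treat linear mixed model of gait velocity at weeks 0 to 4, fitted by REML.

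The Power Analysis in the same section states that for Aims 1 and 2 "the power analysis was based on a LMM with two treatment groups and 5 repeated measures", at a significance level of 0.05. It concludes that "n=80 patients (40 per arm) has 92% to 94% power to detect an effect size/improvement of 35"%, with the variance running from 0.17 to 0.15. It says the total was deliberately raised "to examine modifying factors, such as TA MEP (primary modifying factor), on treatment", and supports this with two figures: "for n=30 per arm the power to determine efficacy (aim 1) is 85"% for a 35% effect, and, at 40 per arm with a smaller interaction effect, "effect size 28% can be detected with 79% power".

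The Aim 2 analysis text says that "a LMM model with three-way interaction (group, time, modifying factor) will be used to test" whether a stroke feature modifies response. The TMS part of the Exclusion Criteria adds that "potential subjects who do not qualify for TMS will not be excluded from the main study"; they only miss the TMS procedures.

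The enrolment table lists 80 (Aims 1 and 2) and 20 (Aim 3) in a column that covers both expected completers and the number needed. The Aim 3 text gives 20 as the number randomised, with 82% power. The Progress Report says enrolment is closed, with 62 randomised in Aim 1 and 10 in Aim 3.

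**The concern.** If the 80 randomised already contain the 10% allowance, the power should be computed on about 72, or on a stated partial-data pattern. If 80 is the number to be analysed, more than 80 should be randomised. The two statements cannot both stand, and the enrolment table does not say which is meant.

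For Aim 2, the extra subjects are justified by a power figure attached to detecting a modifying factor. The power model named has two groups and five visits and no modifier, whereas the planned test is a group-by-time-by-factor interaction. At stake is the reading of a null result: a modifier that fails to reach significance would be judged against 79% power that the text does not establish for that test.

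**Working it through.** **Inputs (Power Analysis).** Control improvement 0.25 m/s over 4 weeks; effect 30%, 35% or 40% of that; variance v = 0.15, 0.16 or 0.17; within-subject correlation 0.95; five visits at times 0 to 4; alpha 0.05. Sidedness is not stated; two-sided is assumed, and it is the variant that reproduces.

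**Formula.** Under compound symmetry the per-subject slope variance is v × (1 − 0.95)/10, where 10 is the sum of squared deviations of times 0 to 4. With n per arm, the SE of the 4-week difference is 4 × √(2 × v × 0.05/10/n). Power = Φ(difference/SE − 1.96).

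**Reproducing the plan.** At n = 40 and v = 0.16, SE = 4 × √(0.0016/40) = 0.0253 m/s. For 35% the difference is 0.35 × 0.25 = 0.0875 m/s, and 0.0875/0.0253 − 1.96 = 1.50, giving 93.3% (stated 93.5%). For 28% the difference is 0.07 m/s, giving 79.0% (stated 79%). At n = 30 and 35%, SE = 0.0292, giving 85.0% (stated 85%), so that figure is correct at its own total of 60.

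**Power by number analysed** (columns are v = 0.15/0.16/0.17):

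| Effect | Stated | 40 per arm | 36 per arm |
|---|---|---|---|
| 30% | 87.3/85.2/83.0 | 86.5/84.2/82.0 | 82.8/80.3/77.9 |
| 35% | 94.5/93.5/92.1 | 94.7/93.3/91.9 | 92.3/90.7/88.9 |
| 40% | 98.3/97.7/97.0 | 98.3/97.7/97.0 | 97.2/96.3/95.3 |
| 28% (v = 0.16) | 79 | 79.0 | 74.7 |

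All nine Table 1 cells agree within about 1 point at 40 per arm. At 36 per arm (80 × 0.9/2) the 30% and 35% rows do not.

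**Partial data.** If the 10% drop out with last visits spread evenly over times 0 to 3 (assumption), the mixed model gives 92.9/91.3/89.6% for 35%, and 75.6% for 28% at v = 0.16. The 36-per-arm figures are therefore lower bounds, though close ones.

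**Aim 2 interaction.** For a binary modifier split 50/50 (assumption) the SE of the interaction is twice that of the two-group contrast: 2 × 0.0253 = 0.0506. Then 0.07/0.0506 − 1.96 = −0.58, about 28% power at 40 per arm. At 80 subjects, modifier prevalence from 50% down to 20% gives 28% down to 20%. For a continuous modifier scaled to SD 1, the interaction SE per SD is 4 × √(4 × 0.0008/80) = 0.0253, so 28% per SD would again give 79%. The text states neither a scale nor a prevalence.

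**Aim 3.** f² = 0.16/(1 − 0.5 − 0.16) = 0.471, λ = n × f², F(1, n − 5). At n = 20, λ = 9.41 and power is 81.8% (stated 82%). At n = 10, λ = 4.71 and power is 42.0%.

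**Aim 1 at achieved enrolment.** With 62 randomised (31 per arm assumed, no loss), power for 35% is 88.2/86.1/84.0%.

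**Unit.** The variance is printed in m/s. Read as an SD, 0.16 gives power of nearly 100%; only (m/s)² reproduces Table 1.

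**The case against.** The strongest reply is that nothing important changes for the primary question. The total was deliberately inflated, the plan itself reports 85% at 30 per arm, and 72 completers exceed that case. The mixed model keeps dropouts' early visits, and the 10% has no stated time point, so some of it may fall after week 4. All of this stands. It limits the size of the problem but does not reconcile the two statements.

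On Aim 2, the plan calls the effect an interaction, and several candidate modifiers (gait velocity, range of motion, sensory score) are naturally continuous. A reader might infer that the 79% is definitely not the interaction's power. The documents do not support that: 28% per SD of a continuous modifier gives the same number, and the coding of the TA motor evoked potential is never given. The Medical Devices section describes TMS as identifying whether a brain-to-muscle connection exists, which suggests presence or absence but does not fix the analysis. What stands is narrower: the figure comes from a model stated without a modifier and is not defined for the test it is meant to support.

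A reader might also infer that Aim 3's 82% is a miscalculation. It is not; it reproduces at the planned 20. The shortfall to 10 is conduct, and the documents set no rule for reading a null result against 82%.

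**Conclusion.** The point holds as an inconsistency in the plan's text. The stated Aim 1 and Aim 2 powers assume no loss, while the stated design includes 10% loss. Against the stated figures the cost is about 2 to 3 points at a 35% effect, 4 to 5 points at 30% (about 1 of which is approximation error, since 40 per arm gives 84.2% against 85.2% stated) and about 4 points at 28%. These are upper limits on the loss, because 36 per arm ignores partial data. They rest on compound symmetry, a linear trend and a two-sided test. The documents do not support calling Aim 1 underpowered.

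The Aim 2 gap is potentially much larger, 79% against about 28%, but that size depends on an assumed evenly split binary modifier. In addition, subjects ineligible for TMS, including those with any history of cortical stroke, stay in the trial without a motor evoked potential. The set for the named primary modifier can therefore be smaller than 80, by an amount the documents do not give.

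As conduct only: about 42% for Aim 3 at 10 subjects, and 84.0 to 88.2% for Aim 1's 35% effect at 62.

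**What to change.** 1. In the Aim 1 text, the Power Analysis and the enrolment table, state whether 80 is before or after the 10% attrition, and restate Table 1 and the 28% figure on that basis.
2. Do not present the 79% as power for the three-way interaction unless the modifier's scale (and prevalence, if binary) is stated and the interaction power is recomputed for it, allowing for subjects without TMS data. Otherwise describe it as a two-group slope contrast with 40 per arm analysed.
3. Beside the planned justification, and marked as achieved enrolment, give the power or expected confidence interval width at 62 and 10. Report Aim 3 as estimates with confidence intervals, and do not read a null result against 82%.
4. Correct the variance unit to (m/s)², which is clerical.

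The cost is a few sentences and a short recalculation. No patients are added and the analysis model does not change. The stated powers become slightly lower for Aim 1; for Aim 2 they may become much lower, depending on how the modifier is defined.
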